## 9.5.7. Prior and Concomitant Therapy

All treatments being taken by the patients on entry to the study or at any time during the study in addition to the investigational product are regarded as concomitant treatments and must be documented on the appropriate section of the eCRF. A history of all prior medications needs to be documented to at least 4 weeks prior to study participation, and a history of previous treatments for MS needs to be documented for at least the prior 2 years.

Concomitant treatment with any of the medications listed below is not allowed during the study or some time prior to randomization.

# Medications that must be discontinued prior to randomization and cannot be used during the study:

• Non-lymphocyte-depleting disease-modifying MS agents (e.g., glatiramer acetate, interferons) must be discontinued from signing of informed consent until randomization for a minimum of 2 weeks;

 Treatment with medications with a known impact on the cardiac conduction system (e.g., beta blockers, calcium channel blockers, Class Ia or Class III anti-arrhythmics). A list with examples of prohibited cardiac medications is provided in Table 8 (note that this is not a comprehensive list and other drugs in these classes are also excluded. Refer to the Study Reference Manual and contact the Medical Monitor for further guidance if needed.

# Medications that must be discontinued at least 4 weeks prior to randomization and cannot be used during the study:

- Systemic corticosteroid therapy or ACTH is not allowed within 30 days prior to screening, except for treatment of protocol-defined treatment of relapses (Section 9.1.2.3). Corticosteroids that are by non-systemic routes (e.g., topical, inhaled, intraarticular) are allowed.
- Inducers or inhibitors of CYP3A4 metabolism. A list with examples of medications that may affect the metabolism of RPC1063 is provided in Table 9 (note that this is not a comprehensive list and other drugs in these classes are also excluded. The Medical Monitor should be contacted for further guidance as needed.
- Live vaccines.

# Medications that must be discontinued 3 months prior to randomization and cannot be used during the study:

- Treatment with IVIg or plasmapheresis
- Treatment with other disease modifying therapies (e.g., daclizumab, dimethyl fumarate, laquinimod)
- Teriflunomide. Treatment with teriflunomide is not permitted within 3 months prior to randomization. In addition, if a patient has received teriflunomide treatment within 6 months of randomization either of the two following accelerated elimination procedures must be followed, according to the manufacturer's protocol (Genzyme, 2012).
  - Administration of cholestyramine 8 g every 8 hours for 11 days. If cholestyramine 8 g three times a day is not well tolerated, cholestyramine 4 g three times a day can be used.
  - Administration of 50 g oral activated charcoal powder every 12 hours for 11 days.

If either elimination procedure is poorly tolerated, treatment days do not need to be consecutive.

# Medications that must be discontinued 6 months prior to randomization and cannot be used during the study:

- Immunosuppressive agents (e.g., azathioprine, cyclosporine, methotrexate, or mycophenolate)
- Any other investigational agent

# Medications that cannot be used at any time prior to randomization (i.e. are exclusionary and any prior use is prohibited):

- Lymphocyte-trafficking inhibitors (fingolimod, natalizumab)
- Immunosuppressive agents that deplete lymphocytes (e.g., alemtuzumab, anti-CD4, cladribine, rituximab, ocrelizumab, cyclophosphamide, mitoxantrone)

**Table 8** Examples of Prohibited Cardiac Medications

Pharmaceutical Class	Example Medications
Beta blockers	acebutolol, atenolol, betaxolol, bisoprolol, metoprolol, nadolol, propranolol, sotalol, timolol
Calcium channel blockers	diltiazem, verapamil
Anti-arrhythmic drugs	amiodarone, bepridil hydrochloride, disopyramide, dofetilide, dronedarone, flecainide, ibutilide, lidocaine, procainamide, propafenone, quinidine, tocainide
QT prolonging drugs	Citalopram (>20 mg/day), chlorpromazine, haloperidol, methadone, erythromycin

Table 9 Examples of Prohibited Inducers or Inhibitors of CYP3A4

Pharmaceutical Class	Example Medications
HIV protease inhibitors	indinavir, nelfinavir, ritonavir, atazanavir, saquinavir
Antibiotics	clarithromycin, telithromycin, rifampin, rifamycin
Antifungals	itraconazole, ketoconazole, fluconazole
Anticonvulsants	phenobarbital, phenytoin, carbamazepine
Others medications	nefazodone, pioglitazone, troglitazone, amiodarone,
	cyclosporine
Foods and herbal supplements	grapefruit juice, Seville orange juice, St. John's Wort

Treatment for symptoms related to MS (e.g., spasticity, incontinence, pain, fatigue, and depression) is not restricted but investigators should attempt to keep therapies or treatments reasonably constant throughout the study. Patients should have been on a stable dose for 3 months prior to screening. Changes may be made if appropriate for a patient's well-being in the clinical judgment of the treating investigator.

Administration of concomitant medications must be reported in the appropriate section of the eCRF along with dosage information, dates of administration, and reasons for use. For medications with a single active ingredient, generic names for concomitant medication should be used, if possible. For combination products, brand names should be used. The total daily dose should be filled in whenever possible.

#### 9.5.8. Concomitant Procedures

Immunosuppressive procedures that deplete lymphocytes (e.g., total body irradiation, bone marrow transplantation) are not allowed during the study or at any time prior to the study.

Concomitant procedures must be reported in the appropriate section of the eCRF. AEs related to these therapies or procedures must be documented on the patient's eCRF.

#### 9.5.9. Treatment Compliance

It is the Investigator's responsibility to ensure that patients are correctly instructed on how to take their study medication and that each patient is fully compliant with their assigned dosage regimen. Records of study medication used and intervals between visits will be kept during the study. Drug accountability will be noted by the field monitor during site visits and at the completion of the study. Patients will be asked to return all unused medication at the end of the study. The study treatment should be dispensed by the Investigator, or by a qualified individual under the Investigator's supervision. An up-to-date treatment inventory/dispensing record must be maintained as described above in Section 9.5.5.2.

Overall study non-compliance is defined as taking less than 80% or more than 120% of study medication during the entire treatment period.

Details unique to Parts A or B are described below.

#### Part A

At each visit, previously dispensed study medication capsules will be collected by the Investigator and compliance assessed. Patients will record capsules intake in a dosing diary that will be reviewed periodically by site staff and the Clinical Monitor. Patients exhibiting poor compliance as assessed by medication counts (i.e., 2 or more missed medication days in 1 week) and response to the question "Did you take your medication regularly?" should be counseled on the importance of good compliance to the study dosing regimen. Patients who are persistently non-compliant (< 80% or > 120%) should be discussed with the Medical Monitor to determine whether they should be withdrawn from the study.

#### Part B

Compliance with IFN  $\beta$ -1a dosing is to be monitored and recorded by site staff. Patients will record IFN  $\beta$ -1a treatment in a dosing diary that will be reviewed periodically by site staff and the Clinical Monitor.

Compliance with RPC1063 capsules will be assessed as described above for Part A.

#### 9.5.10. Assignment to Treatment

Patients must provide proper informed consent before any study procedures are performed (refer to Section 5.3 for further details regarding obtaining patients informed consent). At the time of consent the patient is enrolled in the study. In Parts A and B patients will be randomized into the study on Day 1 after all screening and baseline assessments have been completed and the Investigator has verified that the patient is eligible per the inclusion (Section 9.4.1) and exclusion criteria (Section 9.4.2).

Randomization will be performed through an IVRS (Section 13.4). Treatment groups are described in Section 9.5.1. Details unique to Parts A or B are described below.

#### Part A

Patients will be stratified by country and will be randomized 1:1:1 to receive placebo, 0.5 mg RPC1063, or 1 mg RPC1063.

#### Part B

Patients will be stratified by baseline EDSS ( $\leq 3.5, > 3.5$ ) and country and will be randomized 1:1:1 to receive IFN  $\beta$ -1a 30  $\mu$ g, or 0.5 mg RPC1063, or 1 mg RPC1063.

#### 9.5.11. Unblinding Procedures for Individual Patients

A patient's treatment group assignment blind will not be broken until the end of the study unless medical treatment of that patient depends upon knowing whether the patient is receiving active drug. In the event that the blind needs to be broken because of a medical emergency, the investigator may unblind an individual patient's treatment allocation. The investigator should attempt to contact the Medical Monitor as soon as practicable to discuss the medical emergency and the reason unblinding. The treatment assignment will be unblinded through an IVRS. Reasons for treatment unblinding must be clearly explained and justified in the eCRF. The date on which the code was broken together with the identity of the person responsible must also be documented.

A PK sample will be obtained whenever possible for patients with any AE resulting in unblinding, discontinuation or SAE.

#### 10. STUDY SCHEDULE

The study design is shown in . Tests and Assessments are outlined in Table 1 and Table 2 (Part A), Table 3 and Table 4 (Part B), and Table 5 (cardiac monitoring during dose titration). Methods of assessment are described in Section 11.

It is recommended that the study visits are scheduled in the morning. At the Baseline visit, and on days of study visits on which a predose PK sample is to be obtained (Part A Week 12 and Part B Month 12), patients should be instructed to withhold the dose and the morning meal until the office visit, and dose will be administered during the visit.

Whenever possible, the sequence of when the efficacy assessments are done (EDSS, MSFC) should remain constant and at approximately the same time of day throughout the study. Assessment of the MSFC should start with walking, and it should be done before walking for EDSS.

Predose blood samples for PK evaluation are to be taken 5 to 30 minutes prior to study treatment administration. Actual sampling times must be accurately recorded in the source document and appropriate eCRF. On days of study visits with collection of predose PK blood samples, patients must arrive at the site in fasting conditions.

On days of study visits on which a postdose PK sample is to be obtained, patient visits should be scheduled so a sample can be obtained 2 to 6 hours after the patient's usual dosing time. The patient should also be instructed to ensure that the dosing time is accurately recorded in the dosing diary.

It is recommended that procedures are performed in the following order (note that not all procedures are performed at every visit):

- Spontaneous or solicited AE reporting
- ECG
- Vital signs
- Clinical laboratory tests, including predose PK sampling
- Physical examination
- Efficacy assessments.

Specified visit windows (other than visits during dose titration) may be extended on a case by case basis if needed to accommodate scheduling *except* for the following procedures:

- Brain MRI
- EDSS and neurological examination

# **10.1.** Screening Period (Part A and Part B)

Every effort should be made to complete all screening procedures within 30 days prior to receiving the first dose of study treatment in Part A or B of the study. If necessary, the Principal Investigator (or designee) may extend the Screening Period if needed to a maximum of 45 days

to accommodate scheduling of screening and baseline procedures. If screening procedures cannot be completed within 45 days, the Medical Monitor must be contacted for approval for any further extension, and to discuss whether any Screening procedures must be repeated prior to randomization. All screening assessments and procedures are to be performed by the Principal Investigator or a qualified designee.

Written, signed, and dated informed consent from the patient prior to the performance of any study-related procedures must be obtained by the Principal Investigator or designee (refer to Section 5.3 for further details regarding obtaining patients informed consent). A copy of the signed informed consent must be given to the patient for his/her records.

#### **Screening Period**

During the screening period, the following procedures will be performed:

- Obtain patient's informed consent
- Inclusion/exclusion criteria
- Complete medical history
- Blood/urine sampling for the following laboratory tests:
  - Hematology: red blood cell (RBC) count, total and differential WBC count (basophils, eosinophils, lymphocytes, monocytes, and neutrophils), platelet count, hemoglobin, hematocrit, mean corpuscular volume (MCV), mean corpuscular hemoglobin (MCH), and mean corpuscular hemoglobin concentration (MCHC)
  - Blood chemistry: sodium, potassium, chloride, calcium, magnesium, phosphate, blood urea nitrogen, random glucose, albumin, alkaline phosphatase, creatinine, SGPT/ALT, SGOT/AST, gamma glutamyltransferase (GGT), amylase, total bilirubin, conjugated bilirubin, hemoglobin A1c. Abnormal laboratory parameters inconsistent with clinical presentation of MS or suspicious of underlying medical condition should be repeated for accuracy.
  - Urinalysis: leukocytes, specific gravity, bilirubin, blood, glucose, ketones, pH, protein, and urobilinogen
  - Serum beta-human chorionic gonadotrophin (β-hCG) (women of childbearing potential only)
  - Coagulation panel: prothrombin time (PT) and partial thromboplastin time (PTT)
  - Sensitive thyroid stimulating hormone (sTSH)
  - Viral serology: HIV antibodies, anti-hepatitis A virus IgM, HBsAg and HBcAg IgM, anti-HCV IgG or IgM. In addition, patients must have documentation of positive VZV IgG antibody status. Patients who are negative for VZV IgG antibodies at screening can undergo vaccination and be enrolled 30 days after appropriate VZV vaccination has been completed. Patients testing positive for HIV or for serological markers of acute or chronic hepatitis A, B, or C will be

excluded from the study unless they are indicative of prior hepatitis B vaccination or cured hepatitis A or B and accompanied by normal liver transaminase values.

- Syphilis RPR. Patients must have a negative result to be enrolled.
- TB testing. TB testing will include the purified protein derivative test. All testing must be completed prior to administration of study drug on Day 1. As available locally, an interferon gamma release assay such as QuantiFERON Gold test or other comparable interferon gamma release assay test (e.g., T-SPOT) may be used as an alternative TB screening test. Patients testing positive for TB with the purified protein derivative skin test or interferon gamma release assay will be excluded from the study unless there is (1) a history of either prior TB vaccination or well-documented cured TB/treatment of tuberculin conversion that is (2) accompanied by a chest x-ray negative for active infection, taking into account the subject's risk for TB based on history of contact, symptoms and physical signs. The investigator should consult an infectious disease physician if needed
- Complete physical examination: including evaluation of heart, lung, head and neck, abdominal, neurological, skin, and extremities. Note: Neurological evaluation should include fundoscopic examination to rule out uveitis and other clinically significant ophthalmologic abnormalities, which should be recorded in source documents.
- Height and weight
- Vital signs: body temperature, blood pressure and heart rate
- Chest X-ray: not required if performed within 60 days prior to randomization and if documentation is on file
- 12-lead ECG: the screening ECG report from the central reader must be available to confirm patient eligibility before randomization
- Enroll patient, contact IVRS
- EDSS and neurological examination
- Brain MRI
- MSFC practice. Three MSFC practice assessments must be performed before baseline: MSFC Practice 1 is to be performed at the screening visit, MSFC Practice 2 and MSFC Practice 3 may also be performed at the screening visit, or on other days between the screening and baseline visit).
- LCLA
- Pulmonary function tests including FEV1 and FVC measurements, and DLCO
- OCT evaluation
- Dermatological examination.
- Suicidality assessment using the C-SSRS

- Record relevant prior and current therapy. A history of all prior medications needs to be documented to at least 4 weeks prior to study participation, and a history of previous treatments for MS needs to be documented for the prior 2 years
- SAEs to be recorded from the time of signing the informed consent; AEs to be recorded from the first dose of study drug.

#### 10.1.1. Screen Failure

A screen failure is defined as a patient who has given informed consent, and failed to meet the inclusion and/or exclusion criteria.

## 10.1.2. Rescreening of Patients

Patients who fail to meet the inclusion/exclusion criteria can be rescreened. The Medical Monitor should be contacted prior to rescreening to discuss whether any prior screening results may still be used for rescreening.

#### 10.2. Part A Treatment Period

#### 10.2.1. Baseline/Day 1 Visit

Eligible patients will be randomized to treatment group on Day 1.

The following assessments will be performed at the baseline/Day 1 visit:

- Review of inclusion/exclusion criteria
- An interim medical history will be performed to complete the screening medical history. Medical events that occur between screening and first dose will be recorded as medical history.
- Blood/urine sampling for the following laboratory tests:
  - Hematology: RBC count, total and differential WBC count (basophils, eosinophils, lymphocytes, monocytes, and neutrophils), platelet count, hemoglobin, hematocrit, MCV, MCH, and MCHC
  - Blood chemistry: sodium, potassium, chloride, calcium, magnesium, phosphate, blood urea nitrogen, random glucose, albumin, alkaline phosphatase, creatinine, SGPT/ALT, SGOT/AST, GGT, amylase, total bilirubin, conjugated bilirubin.
  - Urine beta-hCG (females of childbearing potential only). If the urine pregnancy test is positive, do not dose and confirm with a serum pregnancy test.
  - Standard PK sampling: PK sample is to be taken prior to dose administration
- Weight

- Vital signs: body temperature, blood pressure and heart rate. See the special monitoring procedures below that will be performed on Day 1
- 12-lead ECG. See the special monitoring procedures below that will be performed on Day 1
- Continuous Holter monitoring (15 minutes predose and for 24 hours following dose). See the special monitoring procedures below that will be performed on Day 1
- Randomization
- Dispense study drug (with titration kit) and patient diary, and administer first dose of study drug at the site
- MSFC AND LCLA
- MSQOL-54
- Suicidality assessment using the C-SSRS
- Record concomitant therapy
- Record AEs/SAEs

### 10.2.1.1. Guidelines for Monitoring Patients Taking Their First Dose of RCP1063

On Day 1 of treatment, careful cardiac monitoring of the patients is required. The treating physician is responsible for monitoring the patient following the first intake of the study drug, as well as managing bradycardia symptoms should they occur. He or she must review the baseline predose ECG, vital signs during the 6-hour monitoring period, post-dose ECG, and assess discharge status at 6 hours after dosing. Baseline predose ECG should be provided by the site and be available for comparison to the postdose ECG in order to determine if criteria requiring extended monitoring are met. In addition, continuous Holter monitoring will be performed beginning 15 minutes predose and for 24 hours after dose administration. Further details on ECG and Holter monitoring procedures are provided in the Holter Manual.

Heart rate, blood pressure, and other vital signs will be measured before the first dose of study drug, then every hour for at least 6 hours thereafter (by the treating physician or an assisting nurse). Blood pressure and heart rate will be measured in the supine position and then the standing position at each time point. When obtaining the predose heart rate before the first dose, the patient should be allowed to rest in the supine position for 10 to 15 minutes before taking the heart rate. The supine heart rate and blood pressure measurements should be repeated 2 additional times to produce 3 readings for both heart rate and blood pressure (before the first dose of study drug only). The lowest predose value of supine heart rate and blood pressure (based on systolic blood pressure) will be recorded in the case report form and should be used for comparison to the postdose values. Orthostatic blood pressure will then be measured once with the patient in the standing position (after standing for 2 minutes) before the first dose of study drug.

Patients should receive the first dose of study drug in a fasted condition before 12:00 pm (noon) in the clinic. The first dose of RPC1063 should be administered in a setting in which resources to appropriately manage symptomatic bradycardia are available. A member of the Investigator team

should be available to monitor the patient for the 6 hours monitoring period and will need to report any abnormalities to the treating neurologist. Atropine needs to be readily available to the site personnel.

Additional extended monitoring should be instituted until the finding has resolved in the following situations:

- The heart rate 6 hours post-dose is < 45 bpm
- The heart rate 6 hours post-dose is at the lowest value post-dose (suggesting that the maximum PD effect on the heart may not have occurred)
- The ECG 6 hours post-dose shows new onset second degree or higher AV block
- The ECG 6 hours post-dose shows a prolonged QTcF interval (>450 msec males, >470 msec females).

Should post-dose symptomatic bradycardia occur, the treating neurologist should be notified and he or she should initiate appropriate management, begin continuous ECG monitoring, and continue observation until the symptoms have resolved.

Should a patient require pharmacologic intervention for symptomatic bradycardia, continuous overnight ECG monitoring in a medical facility should be instituted, and the first dose monitoring strategy should be repeated the following day (Day 2). The first dose monitoring strategy should also be repeated at Day 5 if any cardiac safety issues were observed on Day 1.

Patients should have written instruction on when to return to clinic and a 24-hour contact phone number to call in the event of any new or warranted symptoms (e.g., chest pain, dizziness, palpitations, syncope, nausea, vomiting). Patients should be instructed not to drive on the same day after the first dose of study drug administration.

First dose monitoring procedures will also be followed at the Week 24 visit in Part A for patients who elect to continue in the blinded extension study, or for any patient who resumes treatment after missing more than 7 consecutive doses.

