Dose titration was studied, consisting of doses of 0.3 to 2 mg that were increased over a 10 day dosing period, to evaluate the effect on mitigating effect on HR. The nadir HR on each dosing day decreased more on Day 1 among subjects who received RPC1063 (-7.6 bpm) than for placebo (-2.8 bpm). With continued dosing, there was an additional mean decrease of approximately 1-2 bpm per day in RPC1063-treated subjects over Days 2 to 4, with negligible further reduction observed after Day 4 despite administration of higher doses of RPC1063. Smaller change from baseline HR was observed during titration to the 1 and 2 mg doses than change that was observed on Day 1 in the fixed dose regimen. These data suggest that dose titration of RPC1063 does attenuate effects on HR observed at higher doses of RPC1063 treatment.

A second Phase 1 study that was completed, RPC01-102, was a a single-center, double-blind, randomized, placebo- and positive-controlled, parallel-group, nested crossover for positive control, thorough QT/QTc (TQT) study in healthy men and women aged 18-45 years. The study tested the effects of RPC1063 at the intended therapeutic dose (1 mg/day) and at a supratherapeutic dose (2 mg/day) compared with matching placebo. A dose of 400 mg moxifloxacin will be included as a positive control.

The study ruled out a clinically relevant effect on cardiac relevant repolarization at both the 1 mg and 2 mg doses. No new safety signals were identified and adverse events were generally similar to those observed in the previous Phase 1 study (RPCS 001). Further details are provided in the current Investigator Brochure.

Overall, the safety experience with RPC1063 supports its continual development in relapsing multiple sclerosis (RMS) patients.

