#### **Vital Signs**

Blood pressure, heart rate and body temperature will be assessed.

For the Baseline (Day 1) visit and during dose titration (Day 5 and Day 8, as applicable), vital signs should be recorded after the patient has been supine for 10-15 minutes, systolic and diastolic blood pressure and heart rate will be measured 3 times using an automated validated device. The repeat measurements will be made at 2-minute intervals and the lowest of the 3 measurements will be recorded on the eCRF, based on systolic BP. For all other visits, vital signs will be assessed once and recorded on the eCRF.

In case the cuff sizes available are not large enough for the patient's arm circumference, a sphygmomanometer with an appropriately sized cuff may be used. Orthostatic blood pressure will then be measured once with the patient in the standing position (after standing for 2 minutes). A sudden, significant fall in blood pressure (>20 mmHg) between 2 and 5 minutes after standing from the supine position will be interpreted as an orthostatic hypotension and will be documented in the patient chart and eCRF.

Patients will be carefully monitored after the first dose of study medication with a 6 hour post-dose monitoring period of hourly recording of orthostatic blood pressure.

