## 10.3. Vital Sign Measurements

Vital signs including sitting systolic blood pressure (SBP), sitting diastolic blood pressure (DBP), body temperature, and heart rate (HR) will be recorded on the eCRF once per visit. In addition, pre-dose and hourly cardiac monitoring (blood pressures and heart rates) for hours 1-6 will be recorded for all patients at the Baseline visit. Sitting blood pressures will be recorded at each hour and in addition, standing blood pressures will be recorded at Hour 0 and Hour 6 for orthostatic changes.

Summary tables including actual values and change from Baseline (defined as pre-dose on Day 1) values will be presented for vital signs including SBP (sitting and standing), DBP (sitting and standing), temperature, and HR by treatment group for the Safety population. On Day 1, hourly changes from pre-dose in blood pressures and heart rates will be shown for all patients. For all other visits only a single timepoint will be collected and shown.

For patients requiring extended cardiac monitoring due to cardiac safety issues observed in the first 6 hours on Day 1, a listing will be provided that shows the hourly change from

pre-dose assessment through the last hour of cardiac monitoring by patient for heart rate and blood pressure.

Box plots will be provided to display the distribution of vital signs. In addition, line plots will be created to display the change from Baseline over the entire study period (not including Day 1) and separately for change from pre-dose in vital signs for the Day 1 visit.

The number and percentage of patients with SBP > 180 mmHG or < 90 mmHG and HR < 40 beats per minute will be summarized by visit for each treatment group. The number and percentage of patients with clinically relevant abnormalities will be presented by treatment group. The criteria for clinically relevant abnormalities are shown in the following table. Vital signs will be presented by patient in listings.

Vital Sign	Criteria for Abnormalities			
Temperature >38.5°C and an increase from pre-dosing of at least 1°C				
	>120 beats per minute post-Baseline, or			
Heart Rate	an increase from pre-dosing of more than 20 beats per minute, or			
Ticart Rate	<45 beats per minute post-Baseline, or			
	a decrease from pre-dosing of more than 20 beats per minute			
	>180 mmHg post-Baseline, or			
Systolic Blood Pressure	an increase from pre-dosing of more than 40 mmHg, or			
Systolic Blood I lessure	<90 mmHg post-Baseline, or			

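### The Day 1 predose baseline for vital signs is the lowest of three readings, set against later values that appear to be single readings, so mean change from predose is biased toward a smaller fall.

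*Protocol*

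**What the plan says.** Protocol 10.2.1.1 has the predose supine measurements "repeated 2 additional times to produce 3 readings for both heart rate and blood pressure (before the first dose of study drug only"). It continues: "The lowest predose value of supine heart rate and blood pressure (based on systolic blood pressure) will be recorded in the case report form", and adds that this value "should be used for comparison to the postdose values". Postdose vital signs are taken "then every hour for at least 6 hours thereafter", with no mention of repeats. Protocol 10.3.1 sends Part B sites to the same section for Day 1.

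Protocol 11.2.1 (Vital Signs) is worded differently. It calls for three measurements at the Day 1 visit and on Days 5 and 8 where applicable, without restricting them to predose, and "the lowest of the 3 measurements will be recorded on the eCRF, based on systolic BP". At all other visits vital signs are measured once.

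SAP 10.3, which covers Part B only, defines the vital-sign baseline as predose on Day 1 and uses it in the change tables. It adds: "On Day 1, hourly changes from pre-dose in blood pressures and heart rates will be shown for all patients". Its table of clinically relevant abnormalities includes "a decrease from pre-dosing of more than 20 beats per minute" for heart rate and a systolic fall of more than 30 mmHg. It describes blood pressure as sitting, where the protocol says supine.

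**The concern.** A minimum of several noisy readings is not comparable with one reading. It lies below the patient's usual level at that moment even if nothing has changed. With such a baseline, every later single reading looks on average a little higher relative to predose than it is, and mean falls come out too small.

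First-dose heart-rate reduction is an adverse event of special interest (Protocol 9.1.2.5 and 12.4), and it is the stated reason for the titration (Protocol 9.2). For this outcome the bias errs toward reassurance. The selection rule is also unclear: the qualifier about systolic pressure leaves open whether the heart rate entered is the lowest of the three or the one that accompanied the lowest systolic value. Sites could apply the rule differently, and the discarded readings cannot be recovered from the eCRF.

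**Working it through.** The plan gives no figure for this bias and no within-session SD, so there is nothing to reproduce.

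**Inputs from the documents.** Three predose readings, lowest kept, predose only (Protocol 10.2.1.1); hourly postdose readings, inferred to be single; change from predose as the analysis (SAP 10.3).

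**Assumptions.** Readings within the predose session are independent and normal about the patient's level, with no trend. The reading-to-reading SD of heart rate is 2 to 5 bpm. The within-session correlation of heart rate with systolic pressure is rho.

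**Step 1: expected minimum.** For three standard normal readings, E[min] = −3/(2√π) = −0.846. The baseline is therefore 0.846 × SD too low. A single postdose reading is unbiased, so the mean fall is understated by the same amount.

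**Step 2: heart rate under the two selection rules.** If the lowest heart rate is kept, the bias is 0.846 × SD. If the reading is chosen on systolic pressure, it is 0.846 × rho × SD.

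| Assumed SD (bpm) | Lowest heart rate kept | Chosen on SBP, rho 0.5 | Chosen on SBP, rho 0.25 | Chosen on SBP, rho 0 |
|---|---|---|---|---|
| 2 | 1.69 | 0.85 | 0.42 | 0 |
| 3 | 2.54 | 1.27 | 0.63 | 0 |
| 4 | 3.39 | 1.69 | 0.85 | 0 |
| 5 | 4.23 | 2.12 | 1.06 | 0 |

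In the first column, a true mean fall of 7.6 bpm at a given hour would be recorded as 7.6 − 1.69 = 5.9 bpm at SD 2 and 7.6 − 4.23 = 3.4 bpm at SD 5. Under selection on systolic pressure, systolic pressure itself is biased by 0.846 mmHg for each 1 mmHg of its within-session SD.

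**Step 3: if Protocol 11.2.1 governs all Day 1 readings.** Postdose Day 1 values are then also the lowest of three, and the two selections cancel: −0.846 SD − (−0.846 SD) = 0. Later visits are still single measurements against the same baseline, so their mean changes keep the Step 2 bias.

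**Step 4: mean of three as baseline.** Its expectation is the patient's level, so the bias against a single postdose reading is 0.

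**Step 5: falls above 20 bpm at one hour.** Assume true falls are normal with mean 7.6 and between-patient SD 6 bpm. The true share above 20 is 1 − Φ((20 − 7.6)/6) = 1 − Φ(2.07) = 1.9%.

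| Assumed SD (bpm) | Lowest of three | Mean of three |
|---|---|---|
| 2 | 1.5% | 2.7% |
| 3 | 1.7% | 3.7% |
| 4 | 2.1% | 5.1% |
| 5 | 2.7% | 6.8% |

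The current rule falls on both sides of the true 1.9%, and the mean-of-three baseline lies above it throughout, because reading noise widens the tail. The direction depends on the assumed fall. At 13.2 bpm, the Phase 1 figure for 1 mg without titration (Protocol 7.2.4), the true share is 1 − Φ((20 − 13.2)/6) = 12.9%, against about 9 to 10% with the lowest of three and about 15 to 21% with the mean.

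**The case against.** The strongest reply is that the bias depends on one reading of an ambiguous text. Single postdose readings are inferred. The systolic qualifier may leave heart rate almost unbiased, and Protocol 11.2.1 may make the Day 1 comparison symmetric. This stands as a limit on size. It does not clear the plan: if selection is on systolic pressure, that variable takes the full bias, and if 11.2.1 governs, later-visit changes keep it.

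It is also fair that much of the first-dose safety output does not use this baseline. The extended-monitoring triggers use 6-hour findings without the predose heart rate. SAP 10.3 tabulates the minimum heart rate over hours 1 to 6 in absolute terms. Part A has Holter recording, although Part B does not (Protocol Table 5, footnote 4). All arms share the offset, so it cancels in differences in mean change.

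A reader might infer four stronger things, which the documents do not support:

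- **Every patient's fall is understated.** Even with the lowest heart rate kept, 75% of individual hourly falls are understated and 25% overstated, compared with 50/50 for single readings.
- **The Phase 1 fall of 7.6 bpm would shrink to between 5.9 and 3.4 bpm.** That figure is a nadir change. The minimum of six hourly readings has expectation −1.267 SD. At a constant true postdose rate, a nadir fall from the lowest of three is overstated by (1.267 − 0.846) × SD, or 0.8 to 2.1 bpm.
- **Falls above 20 bpm are undercounted.** Step 5 shows no fixed direction relative to the truth, and the SAP does not say whether one hour or any hour counts.
- **Titration is made to look more protective.** Every RPC1063 patient is titrated, so the trial has no untitrated comparison, and the Phase 1 baseline rule is not given.

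**Conclusion.** The point holds for mean change from predose within an arm. Under Protocol 10.2.1.1 as written, mean falls are understated by about 0.85 within-session SD in the variable that drives the selection. For heart rate that is 1.7 to 4.2 bpm if the lowest heart rate is kept, and 0.85 × rho × SD if the reading is chosen on systolic pressure. The multiplier follows from independent normal readings without trend; the bpm range rests on an assumed SD of 2 to 5 bpm. Applied to hourly Day 1 changes, it also rests on the inference that postdose readings are single. Later-visit changes do not need that inference, because Protocol 11.2.1 states that those visits are measured once.

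No claim is made about between-arm mean differences, absolute heart-rate outputs or threshold counts. Separately, Protocol 10.2.1.1, Protocol 11.2.1 and SAP 10.3 disagree on which Day 1 readings are triplicate and on posture, and leave the selection rule open. This is worth correcting because the unbiased alternative uses readings already taken.

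**What to change.** Record all three predose readings in the eCRF. In SAP 10.3, define the analysis baseline for vital signs as their mean, separately for heart rate, systolic and diastolic pressure. Reconcile Protocol 10.2.1.1, Protocol 11.2.1 and SAP 10.3 on three matters: which Day 1 readings are taken in triplicate, how any single recorded reading is selected, and whether the position is supine or sitting. The SAP should also say whether the fall criterion is judged at each hour or at any hour. Leave the bedside monitoring criteria as they are.

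The cost is a few eCRF fields at one visit and a short SAP definition. Reported mean falls will be larger. More patients will cross the change-from-predose fall thresholds, partly through measurement noise, so the SAP should note this beside those counts.
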